#### *Inclusion criteria:*

1. Calls MotoMeds during operating hours
2. Parent/guardian of a patient participant meeting inclusion criteria
3. Provides written consent (household visit) or waiver of consent of documentation (no household visit).

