#### *Exclusion Criteria:*

5. No consent/waiver of documentation of consent
6. Corresponding child participant does not meet inclusion criteria

*Enrollment estimates:* Enrollment will be determined by the number of eligible patient and parent/guardian participants that contact MotoMeds call center. Based on staff capacity, advertising will be controlled to target 3-5 patients per night. As such, a minimum of 819 and a maximum of 1365 patient and parent/guardian participant pairs will be enrolled. We estimate that loss of follow up at 8-12 days will be 10% (Figure 2). Repeat patients within

**Figure 2.** CONSORT recruitment, enrollment, and analysis figure for patient participants.

30 days will be excluded from analysis; other repeat patients will be considered unique participants.

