### **6.6.3 Parent/guardian participants not receiving a household visit**

For parent/guardian participants that are not receiving a household visit due to danger signs present, met capacity, or failed/declined delivery, a waiver of documentation of consent will be presented at the time of the initial call or at the time of the follow-up call (either 24-hour or at the 8-12-day follow-up call). The rationale for the waiver of documentation of consent is that the survey questions pose no more than minimal risk and written consent is not logistically feasible. Explanation of informed consent procedures may be obtained in English (official language of Ghana) or another locally spoken language (ex: Ga) in which the EMT obtaining consent and the participant providing consent are fluent as is common research practice in Ghana (see Gamada Letter of Support).

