## **7. Data Safety Monitoring Committee**

---

Similar to the iteration of this study that was conducted in Haiti, this study is considered minimal risk and a DSMC is not required, unless instructed by the IRB.

A Medical Advisory Committee consisting of Ghanaian and University of Florida physicians specializing in emergency medicine, prehospital medicine, infectious disease, and pediatrics will be convened. The Medical Advisory Committee will receive biweekly email updates including case summaries and relevant medical questions for discussion.

Severe adverse events will be reported per protocols of the Ghana Health Service Ethics Review Committee and the UF IRB. SAE will be defined as: Any event that results in death, significant disability, incapacity, and/or life-threatening situation that developed after enrollment of any patient within the enrollment period (enrollment to the 8-12 day follow-up call). In the event of an SAE, the paramedic supervisor, on-call physicians (primary and secondary), and study director will be notified immediately. NAS leadership and UF leadership (PIs) will be notified the following morning. The leadership will review the situation, dispatch a team to conduct an on-site review/verbal autopsy of the case, and notify the clinical advisory committee. A verbal report will be made to the Ghana IRB within 3 days per their requirements. A preliminary written report will be submitted to both the Ghana IRB and the USA (UF) IRB within five days, as well as the clinical advisory committee. After IRB review and recommendations, a final report will be submitted. The study will continue, be amended, suspended or terminated based on this review process. Given high rates of morbidity and mortality among the participant population and prior research that found the mortality rate in an INACT2 TMDS model in Haiti to be one in 391 participants (0.2%), we anticipate in a population of 891 enrollment participants there will be two mortalities. The threshold for suspending the study for review will be 2 mortalities per two hundred patients enrolled (1%).

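### Where consent for unvisited families is deferred to a follow-up call, a death can drop out of the suspension threshold, serious adverse event review and the 8-12 day outcome if the family declines or is never reached

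*Combined protocol and SAP*

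**What the plan says.** All references are to the combined protocol and SAP.

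- **Suspension rule (section 7).** "The threshold for suspending the study for review will be 2 mortalities per two hundred patients enrolled (1"%). The sentence gives no time window and does not say who counts as enrolled.
- **SAE definition (section 7).** A qualifying event is one "that developed after enrollment of any patient within the enrollment period (enrollment to the 8-12 day follow-up call").
- **Timing of consent without a visit (section 6.6.3).** For parents or guardians "that are not receiving a household visit due to danger signs present, met capacity, or failed/declined delivery", the waiver of documentation of consent is "presented at the time of the initial call or at the time of the follow-up call (either 24-hour or at the 8-12-day follow-up call").
- **Consent as a condition (section 6.5.2).** Parent/guardian inclusion requires: "Provides written consent (household visit) or waiver of consent of documentation (no household visit"). The matching exclusion reads "No consent/waiver of documentation of consent".
- **What happens without consent (sections 6.8 and 6.11).** If a family declines, care is still given but the encounter is not study data. Records from refusals are kept only to count exclusions and their reasons, and are left out of the analysis.
- **Enrollment count (section 6.5.2).** "Enrollment will be determined by the number of eligible patient and parent/guardian participants that contact MotoMeds call center".

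**The concern.** For a visited child, written consent is obtained in connection with the household visit, near the start of follow-up. For an unvisited child, the decision that determines whether the child is in the study can come 8-12 days later, after the outcome has occurred. Inclusion can then depend on the outcome, because a bereaved family may be harder to reach or less willing to agree.

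Three things rest on the affected count:

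1. The 2-per-200 suspension threshold.
2. SAE notification, on-site review and IRB reporting.
3. The Aim I outcome of clinical status at 8-12 days.

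The unvisited group includes the children triaged as severe. For the threshold, every uncounted death pushes the same way, toward no pause. For the Aim I outcome, the direction of bias depends on which families decline or are lost, and the documents do not say. Section 7 states that no data safety monitoring committee is required unless the IRB instructs otherwise, so the first two items are the review triggers that the plan itself prescribes.

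**Working it through.** **1. The plan's own figures.** The threshold is 2/200 = 1.0%. Section 7 cites one death in 391 in Haiti, printed as 0.2%, and expects two deaths among 891.

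- 1/391 = 0.256%, and 891/391 = 2.28.
- 891 × 0.2% = 1.78.
- With the 819 of sections 6.5.2 and 6.12, 819/391 = 2.09.

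All round to two. The differences between 891 and 819, and between 0.256% and 0.2%, are editorial and do not affect this point.

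**2. The provisions followed in order for an unvisited child.**

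| Step | Section | Consequence |
|---|---|---|
| No visit: danger signs, capacity cap, failed or declined delivery | 6.6.3 | Waiver may be given at the initial, 24-hour or 8-12 day call |
| 24-hour call | 6.7 | Covers severe cases, certain fever cases and unsuccessful deliveries; capacity-capped cases are not listed |
| Family agrees | 6.5.2 | In the study |
| Family declines | 6.5.2, 6.8, 6.11 | Excluded; not study data; not analyzed |
| Family never reached | 6.5.2 | No waiver obtained, so the exclusion criterion applies |

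For severe cases the 24-hour call narrows the gap. For capacity-capped cases, a waiver that is not given at the initial call waits until the 8-12 day call. Section 6.5.2 expects 10% loss to follow-up at 8-12 days. That figure is for all participants, and none is given for unvisited families. No provision says that a death in a family in the last two rows counts for any of the three purposes.

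**3. When enrollment starts.** Section 7 does not define it, and other sections point in two directions.

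- *Initial call.* Section 6.5.2 ties enrollment numbers to contact with the call center. Section 6.16 refers the reader to the data collection section for how long each participant is enrolled, and that section (6.11) allows data collection up to 12 days after the initial call.
- *Consent.* Sections 6.5.2 and 6.6.3 make consent or the waiver a condition of participation and allow it to be deferred. On this reading, deaths before a deferred waiver would fall outside the SAE window.

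Section 6.8 adds doubt about who is enrolled. It says that every patient participant has an in-person exam at home, while section 6.6.3 provides for participants who do not.

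**4. Scale.** With about two deaths expected in the whole study, one omitted death is about half of the expected events. Within a given 200 patients it turns 2/200 = 1.0% into 1/200 = 0.5%.

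The share of deaths that would be lost is not in the documents. As an illustration only, let c be the assumed share of deaths counted and p the true death rate, with independent deaths at a constant rate. The chance of at least two counted deaths in 200 is

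1 − (1 − pc)^200 − 200·pc·(1 − pc)^199.

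| True rate p | c = 1 | c = 0.75 | c = 0.5 |
|---|---|---|---|
| 1/391 | 9.4% | 5.7% | 2.8% |
| 1% | 59.5% | 44.3% | 26.4% |
| 2% | 91.1% | 80.3% | 59.5% |

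If 1 − c is read as the share of deaths in unvisited children with deferred consent, the drops across each row are upper bounds. Families who are reached and agree would be counted, and the waiver may be given earlier.

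**The case against.** A reader might infer more: that a family consented at the 8-12 day call has an SAE window of zero length, so that no death there can ever qualify. The documents do not establish this. It requires enrollment to mean consent, which no section states. Sections 6.5.2, 6.11 and 6.16 together suggest the initial call, and on that reading the SAE window is sound. Section 6.7 also calls capacity-capped families participants while they are still waiting and says their cases are recorded as study data.

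A reader might also infer that the SAE window limits the suspension threshold. The threshold sentence carries no window, so a death whose family later accepts the waiver can still be counted.

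Nor does the remark in section 6.19 that emergency patients are excluded show a contradiction. It sits in a paragraph about comparing phone and in-person assessment, and is compatible with following those patients by phone.

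Other safeguards exist. The Medical Advisory Committee receives case summaries every two weeks, and SAEs are reported under two ethics bodies' own protocols, which are not in the documents. These might bring such deaths to light, but the plan does not link the committee's updates to the threshold.

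What these objections leave untouched is the family that declines or is never reached. Even with enrollment at the initial call, sections 6.5.2, 6.8 and 6.11 remove a family that declines after the outcome is known, and no provision keeps a family never reached in the count.

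**Conclusion.** The concern holds in a limited form. Deferred consent for unvisited families, combined with exclusion for lack of consent, lets inclusion depend on outcome. Deaths in families that decline or are never reached can be left out of the threshold count, SAE review and the Aim I outcome at 8-12 days. Separately, the start of enrollment is undefined. The better-supported reading makes the SAE window sound, but the text also permits one that does not.

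The size cannot be derived, because the share of deaths in unvisited children with deferred consent is not given. The percentages above rest on assumed values of c. The conclusion rests on the text and does not depend on them. The point should be corrected; it does not show that deaths will be missed. The 2-per-200 value and the response to it are not questioned.

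**What to change.** 1. In section 7, state that for SAE reporting and for the suspension threshold, time zero is the initial call for every eligible child in the delivery zone, visited or not, whenever the waiver is presented.
2. In section 6.6.3, have the waiver presented at the initial call where feasible, which the section already allows, so that inclusion does not depend on outcome.
3. Where consent is never obtained, report to the IRBs, subject to their agreement, a de-identified count of known deaths and of children with unknown status. Section 6.11 already keeps refusal records to count exclusions.
4. Reconcile sections 6.5.2, 6.6.3, 6.8 and 7 on who is enrolled and from when.

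The cost is a few sentences and an IRB submission, with no new visits or staff. Asking for the waiver during a danger-sign call takes call time. Where it is deferred for that reason, items 1 and 3 still account for known deaths and for unknown status.

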## **8. Possible Discomforts and Risks**

### *Discomforts and risks.*

1. Breach of confidentiality.
2. Caller may underestimate severity of symptoms. A caller may underestimate the severity of a patient's symptoms, either intentionally or unintentionally, leading to an enrollment that does not meet inclusion criteria. This may result in a delay of seeking immediate care for a true emergency.
3. Financial cost. Seeking care at night at established health facilities is expensive. If we conservatively recommend seeking emergency care but the patient does not have an emergency, this will create unnecessary financial burden for the family.

### *Efforts to minimize risk.*

1. To address risk of breach of confidentiality, paper-based data collection will be minimized and when possible, secure electronic-based data collection tools will be used (REDCap). All staff will be trained in the protections of personal information as well as protections of human subjects research. All paper-based documents will

be maintained in a locked cabinet in a secure building with keyed-access limited to study leadership.

2. To minimize understating disease severity, the guidelines for diverting callers directly to a healthcare facility will adhere to established guidelines (e.g. WHO IMCI). The approach will draw on best practices to interrogate callers and have scripts that ask clear dichotomous questions. The study data will be monitored to determine the concordance between phone and household assessments.
3. When directing callers to seek immediate care at a medical facility, study staff will be clear that they are providing qualified recommendations based on the relayed information, but the final decision is the responsibility of the family. Given the conservative approach, we acknowledge that a small percentage of families may experience unnecessary cost exposure which is weighed against the benefit of likely reducing overall morbidity and mortality.

## 9. Possible Benefits

### *Direct:*

The primary direct benefit to study participants is access to qualified healthcare during nighttime hours, when alternative healthcare options are scarce.

### *Indirect:*

The service may decompress high morning caseloads at area hospital and clinics by addressing urgent care needs overnight.

The study has potential to benefit the larger regional, national, and international communities, as it could lead to a sustainable option for nighttime pre-emergent healthcare.

## 10. Conflict of Interest

None. The study investigators and affiliates hold no patents or stock in related technologies.

